- f) Satiety will be measured in length of time of fullness at Ad-libitum meal
- g) Self-administered questionnaires assessing affect, physical activity, attitudes, body image, and eating behavior;
- h) Plasma gastrointestinal hormones (Total and active Ghrelin, GLP-1, CCK, PYY and bile acids) by RIA
- i) Targeted Metabolomics
- j) Blood DNA stored
- k) Stool sample stored
- l) Saliva samples stored
- m) Flexible sigmoidoscopy and biopsies of left colon for mRNA, DNA, protein studies
- n) Pseudo-continuous arterial spin labeling (pCASL) functional brain MRI study paradigm

Medication selection by a non-study pharmacist will be randomized and double blinded (physician, study team and participant) according to the FDA-approved medicine suggested by the phenotype or to another FDA-approved medicine not suggested by the phenotype.

Follow-up: All participants will be seen at 4 and 12 weeks (+/- 4 days) (current standard of practice). All participants will receive standard intense lifestyle interventions, which consists of one visit with CRTU registered dietitian. At 10 weeks (+/- 2 weeks) of treatment, participants will have a repeat flexible sigmoidoscopy and a pCASL functional brain MRI study paradigm. At the 12-week visit, participants will be unblinded to their “obesity-related phenotype” and they could contact their physician to discuss continuation of a FDA-approved medication as clinically indicated and recommended by their physician. Study team will prospectively follow the patients’ weight and waist circumference, as well as any pharmacotherapy followed for obesity every 3 months for 1 year.

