The unique quantitative data garnered in our preliminary studies led to the **overall hypothesis** that weight loss with pharmacological agents may be individualized, based on the baseline abnormality in obesity phenotype of each patient. Thus, each baseline trait could be targeted by pharmacological actions of specific obesity medications.

Hypothesis: We **hypothesize** that the identification of the obesity phenotype at baseline to guide obesity pharmacotherapy will enhance the weight loss response rate (i.e. percentage of patient with weight loss higher than 10% at 12 weeks).

Aim: In a 12 week, randomized, double-blinded, **active** controlled trial, with open-label 9-month extension of 250 participants with obesity; we will compare the weight loss response rate to obesity-phenotype-guided pharmacotherapy (intervention) vs. non-phenotype guided (randomly selected) pharmacotherapy (control) in patients with obesity and an abnormal obesity-related phenotype.

-Sub-aim 1: to study the effect of phenotype-guided pharmacotherapy in brain blood flow and gut mucosal changes.

SIGNIFICANCE

This proposal addresses a significant unmet public health need: the development of effective management approaches to treat obesity based in individual phenotypes. Currently, there are several safe and effective FDA-approved medications and devices for the treatment of obesity. Unfortunately, the response to obesity treatment (medicines, devices or surgery) is highly variable. Obesity phenotypes can be used to predict weight loss response to pharmacotherapy and devices. Thus, it essential that we understand the predictors of response to each intervention for obesity to be able to select the right tool for the right patient with minimal or no side effects – Individualized approach for obesity.

RESEARCH PLAN

Study Design:

[figure not shown]

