Medication selection: Once the phenotype tests are completed the results will be filled in an algorithm to assist on the decision of the medication selection based on our previous data [3, 5, 11, 13]. The algorithm for phenotype selection will be based on the following decision tree (as figure below) 1) Participant will complete the ALL phenotype testing; 2) abnormal phenotype will be selected if participant meets criteria for one variable greater or lower than 90% of median (values described in table below); 3) if match to two or more abnormal (90% percentile) values, participant will be excluded; 4) if no abnormal ($<$ or $>$ 90%) value, the abnormal phenotype will be selected based on the value with $<$ or $>$ 75%; 5) if there are two or more abnormal values (75% percentile), patient will be excluded; 6) if participants do not have any abnormal value (based upon 90% of 75%) will be excluded.

TEST	Abnormal result					Example	Example	Example	Example
	Females		Males			1	2	3	4
	(90%)	(75%)	(90%)	(75%)	Female	Male	Male	Female	
Satiation (Ad libitum)	> 1065 kcal	> 894 kcal	> 1962 kcal	> 1376 kcal	1400 kcal	1000 kcal	1100 kcal	850 kcal	

Buffet Meal)								
Satiety (Gastric emptying SGE $T^{1/2}$)	< 97 min	< 101 min	< 76 min	< 86 min	102 min	80 min	105 min	110 min
Behavioral Traits (Questionnaires)	HADS > 9 points	HADS > 7 points	HADS > 10 points	HADS A > 7 points	5	4	9	3
Energy Expenditure (Resting EE)	< 93% predicted	< 96% predicted	< 88% predicted	< 94% predicted	102%	98%	95%	92%
Phenotype				-	Ab Satiety	Ab Satiety	Ab Psych	Ab E.E.

Once the decision is made on the “phenotype-guided” medication, pharmacy will assess whether patient is randomized to “intervention” or “control”. Based on the randomization, patient will pick up the prescription for 3 months.

Phentermine prescribed subjects will be recommended to involve into resistance training routines. During the 3 month visit, participants will be offered a prescription to continue the medication (if randomized to the intervention group) or switch to the phenotype guided medication (if randomized to the control group). Patients who continue obesity pharmacotherapy will be contacted every three months for one year to monitor their weight and comorbidities.

Control group: Pharmacotherapy for obesity

Standard of care pharmacotherapy for obesity recommends the following doses and regimen for weight loss:

- Phentermine: 15 mg oral daily

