- Phentermine-Topiramate Extended Release (Qsymia®) at dose of 7.5/46 mg oral daily
- Oral naltrexone extended-release/bupropion extended-release (NBSR; Contrave®) at dose of 32/360 mg oral daily (divided in 2 tablets in morning and 2 tablets in evening)
- Liraglutide (Saxenda®) at dose of 3 mg subcutaneous daily

There is currently no gold-standard or first choice for obesity pharmacotherapy and physicians select the medication to use on their patients based on comorbidities, previous experience, safety or adverse events. Thus, in this protocol, the FDA-approved medications will be randomly selected. The physician will review the “selection” to assess for potential contraindications, adverse events and/or drug-drug interactions per inclusion and exclusion criteria.

Intervention group: by obesity phenotype guided pharmacotherapy

Participants in the intervention group will have 4 tests to assess 1) satiation, 2) Satiety/return to hunger, 3) behavioral, or 4) energy expenditure. As described on Figure 8 pharmacotherapy will be guided based on the “abnormal” phenotype (following algorithm described above). In case of a mixed pattern or multiple abnormal phenotypes, patient will be excluded from study and referred to weight management clinic.

Algorithm diagnostic:

1. satiation: Phentermine-Topiramate Extended Release (Qsymia®) at dose of 7.5/46 mg oral daily
2. Satiety/return to hunger: Liraglutide 3 mg SQ daily
3. Behavioral/Psychological: Oral naltrexone extended-release/bupropion extended-release (NBSR; Contrave®) at dose of 32/360 mg oral daily (divided in 2 tablets in morning and 2 tablets in evening); or
4. Energy expenditure: Phentermine 15 mg daily plus increase physical activity and resistance training.

General Principles of Statistical Analyses

Primary endpoint: Total Body Weight Loss, kg (defined as weight changed from baseline to 12 weeks) in the obesity phenotype-guided pharmacotherapy (intervention) vs. the randomly assigned pharmacotherapy (control) group in patients with obesity and an abnormal obesity-related phenotype.

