The secondary end points will be percentage of responders (defined as number of participants who loss 5% or more of total body weight) compared to baseline in the obesity phenotype guided pharmacotherapy (intervention) group vs. standard of care at 4 and 12 weeks; percentage of responders with at least 10 and 15% at 12 weeks, and 10% at 6 months and 12 months; percentage of responders at 5%, 10% and 15%; percentage of responders within each obesity-phenotype group at 4 and 12 weeks; side effects of medications, pharmacogenomics role to weight loss, side effect and; changes in blood flow in the brain areas, and transcriptomic changes in colonic mucosa.; the performance of the PHENO-Test in predicting the obesity phenotype and the weight loss outcome based on the test when comparing phenotype-guided intervention vs. controls. In the open-label extension, we will assess the total body weight loss at 24 and 52 weeks in both groups.

Statistical Analyses: We propose a randomized, double-blinded, active controlled trial of 200 participants with obesity to compare effects of Intervention compared to controls in weight loss. The analysis will involve an ANCOVA models, with the response being actual weight change; the covariates to be considered include gender, and weight at baseline.

Sample size assessment and power calculation: The detectable effect size in weight loss between groups of interest (intervention vs. control) is given in the table below. In our recent pilot study [with Liraglutide 3.0 mg vs. placebo], the SD for the overall weight change (pre-post) observed was 2.8kg [32]. Using this SD, we have estimated the differences between groups that could be detected with approximately 80% power (2-sided α level of 0.05) for main effects. Thus, the sample size needed is 87 participants per group. In order to account for a maximum dropout rate of 13%, we will randomize 100 participants per group. An interim assessment will be done when 50% of the patients have completed the study for the purposes of assessing data quality and the power calculation assumptions. Specifically, that the weight change standard deviation is 2.8 and the dropout rate is 10-13%. No calculation of the treatment difference will be

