done at this assessment. Any suggested revision of the power and sample size calculation based on the standard deviation or dropout rate will be shared with the investigative team - possibly increasing the planned study enrollment. We have no intention of completing the study with less than the original sample size of 100 per group. In the subaim, we will use an ANCOVA to study 20 participants with phenotype-guided pharmacotherapy and compared to 20 participants randomly assigned pharmacotherapy adjusting for their baseline value as a covariate. Additionally, we will study the changes of each drug on treatment compared to baseline using a paired t-test. We noticed a 20% withdrawal rate during the study, we propose to extend to 250 participants enrolled and randomized to reach the 100 participants per group (total of 200 participants) who have completed the study.

Mean difference (Δ) of total body weight loss in controls group (mean average 6.1 kg) vs. intervention group.	Intervention (# of participants)	Control (# of participants)
Mean difference of 10% [6.7 vs. 6.1kg)	343	343
Mean difference of 20% [7.3 vs. 6.1kg)	87	87
Mean difference of 30% [7.9 vs. 6.1kg)	39	39

Anticipated results and significance:

Our study individualizes obesity treatment to maximized pharmacotherapy outcome based on phenotyping obesity at baseline.

Potential pitfalls, precautions taken, and alternative strategies:

- a. Feasibility - Given high volume of patients interested in weight loss, we are confident we will recruit sufficient participants for these studies that involve only noninvasive tests and standard of care treatment.
- b. Statistical power has been addressed with appropriate sample sizes to demonstrate a difference in weight change on NBSR with and with phenotype vs. placebo.

REFERENCE:

1. Apovian, C.M., et al., *A randomized, phase 3 trial of naltrexone SR/bupropion SR on weight and obesity-related risk factors (COR-II)*. *Obesity*, 2013. **21**(5): p. 935-43.
2. Pi-Sunyer, X., et al., *A Randomized, Controlled Trial of 3.0 mg of Liraglutide in Weight Management*. *The New England journal of medicine*, 2015. **373**(1): p. 11-22.
3. Acosta, A., et al., *Quantitative gastrointestinal and psychological traits associated with obesity and response to weight-loss therapy*. *Gastroenterology*, 2015. **148**(3): p. 537-546 e4.

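### The primary ANCOVA is a valid test of guided against non-guided prescribing, but no planned analysis separates a benefit of matching drug to phenotype from the different drug mixes in the two arms

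*Combined protocol and SAP*

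**What the plan says.** The General Principles of Statistical Analyses define the primary endpoint as weight change in kg from baseline to 12 weeks, guided arm against randomly assigned arm. The model is an ANCOVA in which "the covariates to be considered include gender, and weight at baseline"; the Abstract says the same. Neither drug nor phenotype is named.

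The Hypothesis and Aims section gives the rationale that "each baseline trait could be targeted by pharmacological actions of specific obesity medications". Under Intervention group, the algorithm assigns one drug to each of four phenotypes: phentermine-topiramate (satiation), liraglutide (satiety), naltrexone-bupropion (behavioral) and phentermine with resistance training (energy expenditure).

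The Abstract and Study Design give controls "another FDA-approved medicine not suggested by the phenotype". The Control group section says that "the FDA-approved medications will be randomly selected", after which a physician reviews the selection "to assess for potential contraindications, adverse events and/or drug-drug interactions per inclusion and exclusion criteria".

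Three planned analyses come near the matching question:
- The secondary endpoints include "percentage of responders within each obesity-phenotype group at 4 and 12 weeks".
- They also include weight-loss outcome by PHENO-Test, guided against controls.
- For the sub-aim, "we will study the changes of each drug on treatment compared to baseline using a paired t-test".

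**The concern.** In the guided arm, drug shares equal phenotype shares. In the control arm they do not, unless all four phenotypes are equally common. Part of any arm difference may therefore reflect one arm receiving more of a stronger or weaker drug. The same component could also mask a real matching effect.

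What is at stake is attribution. A positive result would support guided prescribing as a policy. Given the rationale, readers will tend to take it as evidence that matching drug to trait works, and the planned analyses cannot show how much of the difference is due to that.

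A smaller point goes with it. Phenotype is established before treatment is assigned, is central to the design and determines the guided drug, yet it is not a named covariate. The covariate list is open-ended, and the omission costs only precision and protection against chance imbalance.

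**Working it through.** **The plan's own figure.** A two-sample t calculation with SD 2.8 kg, two-sided 0.05 and 80% power gives 343, 87 and 39 per arm for differences of 0.6, 1.2 and 1.8 kg. This matches the sample-size table. At 1.2 kg, power is 80% with 87 per arm and 85% with 100 per arm.

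**Drug mix by arm.** Let p be the phenotype shares. Guided drug shares are p. Control shares are (1 - p)/3 if the suggested drug is excluded and the other three are drawn evenly. With no matching benefit, the arm difference from drug mix is the sum of [p - (1 - p)/3] x drug mean, which equals (4/3) x the sum of (p - 1/4) x drug mean. It is zero when every share is 25%.

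**Shares.** The preliminary data give 68/163, 56/164 and 44/164 (published cohort) and 46/165, 46/165 and 56/165 (newer cohort) for satiation, satiety and behavioral. No energy-expenditure share is given; I assume 10% or 25% and rescale the others. At 10%, in the order phentermine-topiramate / liraglutide / naltrexone-bupropion / phentermine:
- Published: guided 0.366/0.299/0.235/0.100, control 0.211/0.234/0.255/0.300.
- Newer: guided 0.280/0.280/0.341/0.100, control 0.240/0.240/0.220/0.300.

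**Drug means.** The Pharmacotherapy table gives losses of 10.9%, 7.4% and 5.4%, with placebo losses of 1.6%, 3.0% and 1.3%. The placebo-subtracted means are 9.3, 4.4 and 4.1. The table has no phentermine row; I assume 3-9%.

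**Worked case** (published cohort, 10% share, phentermine 3%): 0.154 x 10.9 + 0.066 x 7.4 - 0.020 x 5.4 - 0.200 x 3 = about 1.46.

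| Energy-expenditure share | Means used | Published cohort | Newer cohort |
|---|---|---|---|
| 10% | raw | +0.26 to +1.46 | -0.42 to +0.78 |
| 10% | placebo-subtracted | -0.16 to +1.04 | -0.76 to +0.44 |
| 25% | raw | +0.40 | -0.17 |

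Units are percentage points of body weight. At 25% phentermine has zero weight, so its assumed mean does not matter. The narrative means for the first three drugs (9.8, 8 and 8.1%) give -0.12 to +1.28 at 10% and -0.04 to +0.12 at 25%.

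**Can a planned analysis recover the matching effect?**
- *Responders within phenotype.* Each contrast compares one drug with a mix of the others. With the raw means, phentermine set at 5% and no matching effect, the four contrasts in mean loss are 4.97, 0.30, -2.37 and -2.90. Any one alone could look like strong matching or harm. Their equally weighted average is 0.00, so under additive effects pooling would cancel the drug effects. The plan gives no pooling rule or model, and its endpoint is a percentage of responders, not kg.
- *PHENO-Test outcome.* This is again guided against control.
- *Per-drug paired t-test.* This is a pre-post change in the 40-person sub-study, with no matched-against-unmatched comparison.

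**Does a matched term work?** Simulated with no matching effect (raw means, phentermine 5%, published shares, 10%, error SD 2.8), the arm-only model returns 1.04, arm plus phenotype 1.07, and matched plus phenotype plus drug -0.02. Adding phenotype alone therefore does not remove the mix effect. With a true shift of 1.2, the last model returns 1.20 with non-matched controls and 1.21 if controls draw from all four drugs.

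**Power for the matched term** (1.2 kg, SD 2.8, 100 per arm, gender and baseline weight included):
- *Non-matched controls.* Variance is 13-14% higher than for the arm contrast at a 10% share (power 80-81%) and 5-6% higher at 25% (about 84%), against 85% for the arm contrast.
- *Controls drawing from all four drugs.* A quarter are matched by chance, so the arm contrast falls to 0.75 x 1.2 = 0.9 kg, with 62% power. The matched term has 77-78% (10% share) and about 81% (25% share).

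At 87 per arm the matched term has 75-78% against 80% (non-matched), or 71-75% against 56% (random draw).

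**The case against.** The strongest reply is that this is a strategy trial. The aim and primary endpoint compare guided with non-guided prescribing, the ANCOVA tests that, and the sentence about targeting traits is rationale, not an estimand. This stands. It limits the point to interpretation and to a supportive analysis.

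The illustrations are also soft. The phentermine-topiramate figures (10.9% at 15/92 mg, 9.8% at the high dose) are for a different dose from the 7.5/46 mg listed for this trial. The 8.1% for naltrexone-bupropion has no stated time point. The means come from separate trials with different placebo losses. The quoted prevalences are not mutually exclusive, while this trial excludes people who match more than one phenotype. All of this stands, and so none of the ranges is a bound.

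The proposed model has limits too. With non-matched controls, matched status is identical to arm, and it is separated from drug only by assuming additivity. The phentermine term also carries the resistance-training advice. These are reasons to call the model supportive and to state its assumptions.

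Finally, a reader might infer that the option at the 3-month visit to "switch to the phenotype guided medication (if randomized to the control group" contradicts the control definition. It does not: it takes effect at the end of the blinded period and fits controls on a non-matched drug. Random selection in the Control group section may likewise mean random among the remaining drugs. The wording needs clarifying, but it is not a proven contradiction.

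**Conclusion.** The point holds as a gap in interpretation. Randomisation protects the strategy comparison, and the planned primary test is valid for it. What is missing is a prespecified analysis that distinguishes matching from drug mix.

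Two stronger readings are tempting and unsupported. One is that the primary test is biased or has an inflated type I error; it is not, for the question it asks. The other is that drug mix favours guidance by a known amount. The documents give no 12-week mean for each drug, no energy-expenditure share and no phentermine mean, so no 12-week kg figure can be derived. The illustrations span both signs, are small at a 25% share, and vanish if the four phenotypes are equally common. The unequal prevalences quoted in the preliminary data make some difference in mix likely, but not its direction or importance.

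**What to change.** 1. Name the four-level baseline phenotype as a covariate in the primary ANCOVA, for precision and chance imbalance only.
2. Keep the strategy contrast as primary and word its conclusion as a strategy result. Do not attribute benefit to matching from the arm contrast alone.
3. Prespecify, before unblinding, one supportive ANCOVA of 12-week weight change on phenotype, assigned drug (as randomised, before any change from the physician review), a matched indicator, gender and baseline weight. Report the matched term with its 95% CI, drug shares by arm, and the phenotype-by-drug table of numbers and mean loss. State that the model assumes additive phenotype and drug effects and one average matching shift, and that the phentermine term includes the resistance-training advice.
4. Separately, state whether random selection for controls means among the drugs not suggested by the phenotype or among all four, and reconcile the Abstract, Study Design and Control group sections.

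The cost is SAP wording and one extra model, with no new data. With non-matched controls the matched term gives up about 1 to 5 points of power relative to the arm contrast. If controls can draw the matched drug, it gains about 15 to 19 points over the diluted arm contrast (77-81% against 62%). Both comparisons are at 100 per arm with energy-expenditure shares of 10-25%.

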In a 12 week, randomized, double-blinded, active controlled trial, with 9 month open-label extension of 250 participants with obesity; we will compare the weight loss response rate to obesity-phenotype-guided pharmacotherapy (intervention) vs. non-phenotype guided (randomly selected) pharmacotherapy (control) in patients with obesity. All 250 participants will be phenotyped and the medication selection will be randomly and double blinded (to physician, study team and participant) to the FDA-approved medicine suggested by the phenotype or to another FDA-approved medicine not suggested by the phenotype. A computer generated randomization schedule generated by the study statistician's office will be submitted to the Mayo Clinic CCaTS Research Pharmacy. Allocations will be concealed. This study will be blinded until data are transmitted to the statistician for data lock. All participants will receive a standard intense lifestyle intervention, which consists of 1 visit with registered dietitian. The phenotypic studies include (all performed in same day in the following order): Fasting blood collection, resting energy expenditure, gastric emptying

with meal for breakfast, behavioral questionnaires, and buffet meal test for lunch. Blood will be collected assessment of metabolomic biomarkers, gastrointestinal hormones, and DNA (blood and buccal swab). Stool samples for microbiome and bile acid. Saliva samples for assessment of metabolomic biomarkers. Participants will return to the CRTU to pick up medication based on the randomization and a personal fitness tracker. All participants will be seen at 4 and 12 weeks (+/- 4 days) (current standard in practice). Participants will keep a medication diary, which will have to be returned on the 12-week visit. A saliva, stool and fasting blood sample, and DEXA will be done at the 12-week visit. At the 12-week visit, participants will be unblinded to their "obesity-related phenotype" and they could contact their physician to continue a FDA-approved medication as part of clinical care. Study team will prospectively follow the patients' weight, waist circumference and use of obesity medications every 3 months for 1 year. In a sub-study, 40 participants will complete at baseline and at 10 weeks (+/- 2 weeks), a flexible sigmoidoscopy and a pCASL functional MRI; with the intention to study the effects of pharmacotherapy in gut mucosa and brain blood flow changes at baseline and after treatment.

Randomization and Allocation

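### Pitfall (b) claims adequate power for weight change on NBSR by phenotype versus placebo, but the trial has no placebo arm and its only power calculation is for guided versus randomly assigned drug

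*Combined protocol and SAP*

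**What the plan says.** The section *Potential pitfalls, precautions taken, and alternative strategies*, item b, states: "Statistical power has been addressed with appropriate sample sizes to demonstrate a difference in weight change on NBSR with and with phenotype vs. placebo". The repeated word in "with and with" presumably stands for with and without.

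The statistical section describes a different comparison. Under *General Principles of Statistical Analyses*, the primary endpoint is 12-week weight loss in kg "in the obesity phenotype-guided pharmacotherapy (intervention) vs. the randomly assigned pharmacotherapy (control) group in patients with obesity and an abnormal obesity-related phenotype". The *Statistical Analyses* paragraph reads: "We propose a randomized, double-blinded, active controlled trial of 200 participants with obesity to compare effects of Intervention compared to controls in weight loss". The sample-size table that follows has three rows, all intervention versus control: 343, 87 and 39 per group for differences of 10%, 20% and 30% on a control mean of 6.1 kg.

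On treatment, *Study Design* assigns participants to the medicine "suggested by the phenotype or to another FDA-approved medicine not suggested by the phenotype". The *Control group* section lists four active drugs and adds: "Thus, in this protocol, the FDA-approved medications will be randomly selected". In the intervention group, the diagnostic algorithm gives NBSR only to the behavioural/psychological phenotype. Placebo appears only in descriptions of earlier or cited studies.

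**The concern.** Item b is the pitfalls section's assurance that power is adequate, and it attaches that assurance to a comparison the trial cannot make. It differs from the plan in three ways: the comparator (placebo, where the trial uses active drugs), the treatment (one drug, where the trial pools four) and the factor compared (presence of a phenotype on a given drug, where the trial randomises the selection strategy).

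Drug-level and phenotype-level results will be produced. The secondary endpoints include responders within each phenotype group, and the sub-aim plans a paired test for each drug. A reader who relies on item b could take an NBSR or behavioural-phenotype result as adequately powered, or read a null result there as evidence of no effect.

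**Working it through.** **1. Reproduce the plan's figure.** Inputs from *Sample size assessment and power calculation* and its table: SD 2.8 kg, two-sided α 0.05, 80% power, differences 6.7 − 6.1 = 0.6, 7.3 − 6.1 = 1.2 and 7.9 − 6.1 = 1.8 kg.

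Normal approximation: n per group = 2 × (1.960 + 0.842)² × (SD/δ)². For δ = 1.2 this is about 85.5, so 86. The two-sample t-test gives 86.4, so 87. By t-test the three rows are 343, 87 and 39, an exact match. With 87 per group, t-test power is 0.803; with 100 per group it is 0.854. The calculation is for guided versus control, and no other calculation is given.

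**2. Placebo comparison.** The number assigned to placebo is 0. There is no power to compute.

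**3. What the rest of the sentence could mean.** The documents do not define an NBSR or behavioural-phenotype contrast in kg, so these inputs are assumptions:
- Behavioural phenotype share p = 27% to 34%, the prevalences in the two earlier cohorts (*Emotional Hunger Phenotype*). The trial's own mix is not given.
- 100 completers per arm, the plan's target.
- δ = 1.2 kg and SD = 2.8 kg, borrowed from the primary contrast. The documents give no effect size for NBSR.
- Controls take NBSR with probability 1/3 if they draw from the three non-matching drugs (*Study Design*), or 1/4 if they draw from all four (*Control group*).

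Power ≈ Φ(δ / [SD × √(1/n₁ + 1/n₂)] − 1.960). Example, 27 versus 24.3: standard error = 2.8 × √(1/27 + 1/24.3) = 0.783; 1.2/0.783 = 1.533; Φ(−0.427) = 0.335, or 0.324 by t-test.

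| Reading | n₁ v n₂ | Power, normal | Power, t-test |
|---|---|---|---|
| NBSR with v without phenotype, control share 1/3, p = 27% | 27 v 24.3 | 0.335 | 0.324 |
| Same, p = 34% | 34 v 22 | 0.347 | 0.337 |
| NBSR with v without phenotype, control share 1/4, p = 27% | 27 v 18.25 | 0.293 | 0.282 |
| Same, p = 34% | 34 v 16.5 | 0.298 | 0.288 |
| Guided v control within behavioural phenotype, p = 27% | 27 v 27 | 0.350 | 0.340 |
| Same, p = 34% | 34 v 34 | 0.424 | 0.414 |

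Here n₁ = 100p. In the first four rows n₂ = 100(1 − p) × 1/3 or 1/4; in the last two n₂ = 100p. Across the readings, t-test power is about 28–41%. With 87 completers per arm, each figure is lower.

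**4. How far to trust those shares.** In the previously published cohort, the three phenotypes with stated prevalence are 42%, 34% and 27%, which sum to 103% before energy expenditure is counted. The phenotypes therefore overlapped there. This trial excludes people who match two or more phenotypes at the applicable cut-off, and also those with an anxiety or depression score above 11. The cohort prevalences are not shares of the randomised sample.

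**The case against.** The strongest reply is that nothing operative depends on item b. The primary endpoint, the ANCOVA and the sample-size table all describe the same guided-versus-random comparison, and the full power calculation stands directly above the pitfalls section. The sentence is garbled and looks like text carried over from another protocol, although the documents do not say so. This stands, and it is why the point is minor.

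It is also fair to say that the power range in the working is not a property of this plan. Comparing NBSR patients with and without the phenotype sets behavioural participants in one arm against non-behavioural participants in the other, so it is not a randomised comparison, and no section plans it. The effect size is borrowed and the shares come from differently selected cohorts. This stands too: the range shows scale only. It also concerns mean weight loss in kg. The power of the secondary within-phenotype responder endpoints was not computed here, and the plan gives none.

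The reply does not make the sentence true. The missing placebo arm and the mismatch with the primary contrast need no assumption.

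A reader might infer that the trial was sized for the wrong comparison, or that 87 per group is unsound because of item b. The documents do not support this, because the table reproduces for the primary contrast. A reader might also infer that an NBSR-by-phenotype test is a second planned, powered analysis. It appears in neither the endpoint list nor the analysis text.

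**Conclusion.** Item b is wrong as written: it claims adequate power for a comparison that includes a placebo group the trial does not have, on one drug that the power calculation never isolates. This is a minor internal inconsistency, not a calculation error. The primary sample size, endpoint and analysis are unaffected.

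That conclusion rests on the documents' text alone. The size attached to it, roughly 28–41% power, is conditional on behavioural shares of 27–34%, 100 completers per arm, a 1.2 kg difference and an SD of 2.8 kg, and it varies with the reading. The safe statement is that power under each of these readings is far below 80%; no single figure should be cited as the trial's power for NBSR.

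**What to change.** Replace item b with:

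*The sample size gives about 80% power (two-sided 0.05) for the primary contrast only: 12-week weight loss in kg, phenotype-guided versus randomly assigned pharmacotherapy, as calculated above. The trial has no placebo arm, and no single-drug or single-phenotype comparison, including the secondary within-phenotype responder endpoints, was separately powered.*

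This wording points to the existing calculation without restating its inputs. It also avoids calling every phenotype comparison exploratory, which would conflict with the listing of responders within each phenotype group as a secondary endpoint.

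The cost is an edit to one item. No sample size, procedure or analysis changes. The downside for the sponsor is a less favourable statement about power at drug and phenotype level.
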